- 1) What is the annual incidence of revisions of various degrees, and how has the incidence changed during the last 20 years?
- 2) What is the current prevalence of n-grade revisions, and how has the prevalence changed during the last 20 years?
- 3) What is the relationship between the annual incidence of revisions of n-grade with the incidence of primary procedures in the preceding years?

WP-A2: Cumulative Revision Rates (CRR)

The purpose of this WP is to determine the cumulative revision rate (CRR) for revisions of different grades (number of previous revisions) to generate information that can be used for informing patients preoperatively.

Research questions:

1. What is the CRR for n-grade revision?
2. Is CRR influenced by demographic and surgical variables such as sex, age, education, implant type, place of residence, income, operative technical conditions and the indication of revision such as infection, aseptic loosening, instability, pain without reason?

WP-A3: Lifetime risk of multiple revisions

The purpose of this WP is to determine the lifetime risk of revision of various grades as well as the lifetime risk of arthrodesis and amputation. These risks will be investigated in relation to demographic and surgical variables.

Research questions:

1. What is the lifetime risk that a patient with a given combination of demographic and surgical variables will need n-number of revisions after primary arthroplasty?
2. As above but with arthrodesis and amputation as the risk event.

Review of literature

To gather relevant background information for this protocol, MEDLINE via pubmed was searched to find relevant literature in the field. The MESH words "knee replacement" and "reoperation" were used. We wanted to identify articles that either described epidemiological findings regarding multiple revision knee arthroplasties or described risk factors associated with repeated revisions. There were no MESH words containing "rerevision", "multiply revisions" or "repeated revisions".

Articles found: 4350 results.

Based on the title, this number of abstracts were reviewed: 97

Of the abstracts, so many articles were reviewed and read: 65

Number of articles used in the protocol: 47.

Material and methods

Design

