In WP-A1 we want to calculate:

- 1) Annual incidence of revision arthroplasties.

Incidence is calculated as the number of n-grade revisions performed in Denmark during a given year as a proportion of the current year's population. This is done for each level of revision.

The incidence rate is also calculated:

$$IR = \frac{\text{Number of } n\text{-grade revisions}}{\text{Number of person-years in observation period}}$$

- 2) The continuous prevalence of revision knees.

Prevalence is calculated as the number of patients living with n-grade revision knee as a proportion of the current year's population. This is done for each level of revision.

- 3) The relationship between the annual incidence of n-grade revisions with the incidence of primary procedures in the preceding years.

$$\text{rate ratio} = \frac{\text{IR for } n - \text{ grade revision}}{\text{IR for primary procedures the previous year}}$$

WPA2

The analyzes will be based on the population defined in WP-A1. We will estimate the cumulative incidence (risk) for the different levels of revision and examine whether factors such as patient demographics, implant type and other operative technical conditions influence the cumulative incidence.

$$\begin{aligned} & \text{risk for } n - \text{ grade revision} \\ & = \frac{\text{number of } n - \text{ grade revisions in the observation period}}{\text{numbers with } n - 1 \text{ revisions}} \end{aligned}$$

To investigate whether patient demographics, implant type, indication for revision and other operative technical conditions have an effect on the subsequent incidence of revision, we will use regression analysis. It will be relevant to investigate possible confounding of the variables.

In addition, we will create "cumulative incidence plots" for each level of revision to illustrate prosthesis survival.

WPA3

The lifetime risk will be determined as a summation of the expected remaining life based on the CRR for the individual events (primary procedure and n-grade revision). As in WPA2, we will examine whether patient demographics, implant type and other operative technical conditions have an effect on the risk of revision. In addition, the lifetime risk of arthrodesis or amputation as an event will also be calculated. Thus, data from WP-A2 becomes the starting point for the calculations.

Applicant's duties

The applicant's duties consist of:

The overall responsibility for the execution of the project.

Obtaining necessary data approvals.

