## 1. STUDY OVERVIEW

---

**Background and rationale** Knee arthroplasty is a common procedure performed worldwide to improve the quality of life for patients with degenerative knee conditions, trauma, and tumours. Complications can occur after knee arthroplasty, which may lead to a revision procedure, where at least one implant is exchanged, added, or removed. As the number of primary procedures in the world is increasing, so is the corresponding number of revisions. Some patients may require additional revision procedures, and some may end in a negative spiral of repeated revisions; We define three or more revisions on the same knee as being 'multiply revised'. The clinical impression of multiply revised patients is that the repeated occurrence of complications has significant impacts on the patients' quality of life including chronic pain, decreased independence, and increased morbidity. No study has yet investigated the incidence and prevalence of multiply revised knee arthroplasty patients stratified by previous revisions. To improve the care of multiply revised patients, epidemiological information is required which is the rationale of this study.

**Objectives** The aim of this observational study is to investigate the incidence and prevalence of multiply revised knee arthroplasty patients in all Danish patients with primary knee arthroplasty.

**Hypothesis** The number and burden of knee arthroplasty revision procedures and patients in Denmark has increased dramatically in the last 23 years.

**Methods** This is an observational study. Data will be collected from all primary and revision knee arthroplasties performed in Denmark from January 1st 1998 to 31st December 2021. Data will be acquired from two registers: The Danish Knee Arthroplasty Register (DKR), containing surgeon-reported data on primary and revision knee arthroplasties. In addition, data will be acquired from Landspatientregisteret, which contains all clinical data collected during any visit to a public or private healthcare facility in Denmark.

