### PICOTS

**Population:** All Danish citizens who have received a primary knee arthroplasty at a Danish healthcare facility, from the 1st of January 1998 to the 31st of December 2021

**Intervention/Exposure** Multiple revision knee arthroplasties in the same knee

**Comparator:** None

**Outcome (primary):** Annual standardized prevalence and incidence of n-grade revisions following knee arthroplasty between 1998 and 2021 in Denmark.

**Time:** Retrospectively, from the 1st of January 1998 to the 31st of December 2021, i.e., up to 24 years follow-up.

**Study design:** Observational retrospective register study.

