#### **Data management, for both registers.**

Definition of a revision: A revision is defined as the exchange, addition, or removal of a knee prosthesis component (1). However, knee arthrodesis and amputation are not included in this study.

Definition of major revision: A major revision is defined as exchange of the femoral component and/or the tibial component with subgroups of tibial, femoral and all component exchange (2).

Definition of minor revision: A minor revision is defined as the exchange of polyethylene liner and/or addition or revision of the patella component. Insertion/removal/exchange of spacers are also included in this category (2).

Population: The population is defined as the number of alive citizens in the state of Denmark. Annual populations are defined as the population in Denmark on the 1st of January that year. Additional data for sex and age of the population is acquired. Data for the population is acquired from Danmarks Statistik (3).

In case of disagreement between registers: In cases of discrepancy between the two registers, Landspatientregisteret will overrule the Danish Knee arthroplasty register concerning following variables:

- Laterality
- Date of surgery
- Gender
- Age
- Performing institution

In cases of discrepancy between the two registers, the Danish Knee arthroplasty register will overrule Landspatientregisteret concerning following variables:

- Procedure code
- Revision of tibia
- Revision of femur
- Indication

Calculation of standardized prevalence: Annual standardized prevalence is calculated as the number of patients living with a n-grade revision during a given year as a proportion of the population in Denmark (the 1st of January that year) (3). The prevalence is then multiplied by 100,000 for standardization. This is done for each level of revision, each year. E.g., the standardized prevalence for 1998 is calculated as:

$$\text{Standardized prevalence, 1998} = \frac{\text{Number of knees living in 1998 with a } n - \text{ grade revision}}{\text{Total population in Denmark in 1998}} * 100,000$$

The prevalence is only calculated for revisions performed between January 1st 1998 and December 31st 2021.

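### The SAP gives arthrodesis and femur amputation no role in knee status, so as written a fused or amputated knee keeps its last revision grade in the prevalence numerator until the patient dies or emigrates

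*SAP*

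**What the plan says.** **Protocol.** Under Identification of revision procedures, `KNGG*` (arthrodesis) and `KNFQ19` (femur amputation) are among the codes that build the revision cohort. Description of data from LPR requests both. Organization of data says that the combined table will give the status of every knee on any date, and that it will hold deaths, disappearances and emigration. Question 1 under Purpose asks how many patients live with a multiple revision knee. Research question 2 of WP-A1 asks "What is the current prevalence of n-grade revisions". Statistics, WPA1, states: "Prevalence is calculated as the number of patients living with n-grade revision knee".

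**SAP.** The primary outcome in PICOTS is "Annual standardized prevalence and incidence of n-grade revisions following knee arthroplasty between 1998 and 2021 in Denmark". In section 3, Data management, for both registers, the definition of a revision adds: "However, knee arthrodesis and amputation are not included in this study". The Landspatientregisteret parts of section 3 list `KNGB*`, `KNGC*` and `KNGS49`, but neither salvage code. Prevalence is described in the text as "the number of patients living with a n-grade revision during a given year as a proportion of the population in Denmark", and the numerator of the formula begins "Number of knees living in 1998 with a". The section 2 table lists year of death or emigration, while section 3 elaborates year of death only. Section 4 records no deviation from the protocol.

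**The concern.** A prevalence count needs a rule for entering the numerator and a rule for leaving it. The SAP writes the first (an n-grade revision in the observation period) but leaves the second to death and, by the section 2 table, emigration. Arthrodesis and amputation are the other events after which a knee may no longer be a revision knee in the sense of the protocol's question, and the SAP sets these events aside without saying what they do to status.

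Two analysts could therefore build different numerators from the same data. One follows the SAP as written and keeps a fused or amputated knee at its last grade. The other takes the living-with wording as current status and wants to remove the knee, but finds no code or rule in the SAP for doing so. The annual prevalence series would differ between them, and it is a primary outcome.

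**Working it through.** **Text check.** Set side by side, the passages show three things.

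1. The protocol has the salvage codes in the revision cohort and in the data request. The SAP excludes the procedures and does not name the codes, and section 4 does not log the difference.
2. The exclusion sentence sits inside the definition of a revision. It settles what counts as an event. It does not say what happens to the knee afterwards.
3. No readable passage removes, censors or reclassifies a fused or amputated knee.

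**Size.** The plan states no figure for this, so there is none to reproduce. The inputs all come from the protocol:

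- more than 150,000 primary procedures in about 20 years (Background); 150,000 is used
- first-revision risk of about 13% within 20 years (Size of the problem)
- arthrodesis 0.26% and transfemoral amputation 0.32% of primaries, 1997 to 2013 (Outcome after revision and re-revision)

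Ever-revised knees: 150,000 × 0.13 = 19,500.

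Salvage knees, x:

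- full overlap (every arthrodesis knee later amputated): 150,000 × 0.0032 = 480
- no overlap: 150,000 × (0.0026 + 0.0032) = 870

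Let r be the survival of salvage patients relative to other revised patients. The share of the recorded count that is salvage knees is x·r / (19,500 − x + x·r). The overcount relative to the corrected count is x·r / (19,500 − x).

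| Scenario | Share of recorded count, full overlap | Share of recorded count, no overlap |
|---|---|---|
| All salvage knees previously revised, r = 1 | 480/19,500 = 2.5% | 870/19,500 = 4.5% |
| Same, r = 0.5 (assumption) | 240/19,260 = 1.2% | 435/19,065 = 2.3% |
| r = 0.5 and half previously revised, x = 240 or 435 (assumptions) | 120/19,380 = 0.6% | 217.5/19,282.5 = 1.1% |

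In the first row, the overcount against the corrected count is 480/(19,500 − 480) = 480/19,020 = 2.5% to 870/(19,500 − 870) = 870/18,630 = 4.7%.

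**Limits.** The salvage risks cover 1997 to 2013 and the 13% covers 20 years, so the ratio is approximate. The first row is a ceiling only if salvage patients survive no better than other revised patients. The documents do not give the distribution of salvage knees by grade, so no percentage is offered for grade 3 or more.

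**The case against.** The strongest reply is that the count may be meant as history. SAP section 1 says "We define three or more revisions on the same knee as being" multiply revised, which is a count of procedures, and Figure 3 sums all revisions on a patient. On that reading a patient revised three times and later fused belongs in the numerator, and removing the knee would drop some of the worst outcomes. This reading is tenable, and neither document says outright that salvage ends prevalence status. It does not remove the point. The prevalence wording in both documents is about living with a revision knee, and the SAP never says that history is meant.

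Second, the lists in SAP sections 2 and 3 are not declared closed, a data template is still to come, and the codes have been requested. The Figure 1 flow diagram, which is to show reasons for exclusion, is not visible, so an exclusion there cannot be ruled out. This stands as a limit. Even so, an exclusion would need the same codes and a decision on whether the knee's years before salvage are kept.

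Third, the effect is small, and the study is descriptive with no formal testing. That is also right, and it rules out some stronger conclusions that a reader might draw:

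- *The knees stay until death.* Not supported: the section 2 table also lists emigration, although no rule for using it is written.
- *The omission favours the hypothesis.* The SAP hypothesis is "The number and burden of knee arthroplasty revision procedures and patients in Denmark has increased dramatically in the last 23 years". Retained knees do accumulate over calendar time, but prevalence counts only revisions from 1998 onward, so the whole numerator builds up from that year. A distortion of a few per cent could not produce a dramatic rise.
- *The highest grades are badly distorted.* The protocol describes salvage as the end of repeated revision, so the relative effect may be larger there, but any figure would rest wholly on assumed shares.

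**Conclusion.** The concern holds in limited form. Leaving arthrodesis and amputation out of the revision count is sound. What is missing is their role in knee status. As written, the SAP keeps such knees at their last grade until death or emigration, which does not fit the current-status wording of a primary outcome and departs from the protocol without being logged.

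On the current-status reading the all-grade effect is a few per cent at most: about 2.5–4.5% of the recorded count at the ceiling, and about 0.6–2.3% under the labelled assumptions on survival and prior revision. On the history-based reading there is no overcount, only an unstated definition. The change should be made because it is cheap and alters a primary number, not because the error is large. Confidence is medium, since the intended reading is not stated and the flow diagram cannot be seen.

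**What to change.** Keep arthrodesis and amputation out of the revision count, and make these changes:

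1. **SAP section 2:** add `KNGG*` and `KNFQ19` with date and laterality.
2. **SAP section 3, calculation of prevalence:** state that prevalence is current-status. A knee leaves the numerator at death, at emigration or disappearance, or at arthrodesis or femur amputation on that side. Its years before the exit are kept. It re-enters if a later prosthesis procedure is recorded on that knee.
3. **Secondary figure:** report the ever-revised count among living residents, labelled as such, and label Figure 3 as history-based. Readers then have both quantities.
4. **SAP section 4:** log the difference from the protocol's Identification of revision procedures.
5. **Emigration:** align the year-of-death entry in section 3 with the section 2 table.

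The cost is modest. The codes are already requested, and the lifetime-risk package (WPA3) needs them for arthrodesis and amputation. The work is one status rule, one merge and one extra labelled series. Prevalence becomes slightly lower, and salvage codes without laterality need a stated handling rule, with their number reported.

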Landspatientregisteret (LPR) is a national and clinical database administered by the Danish Health Authority since 1976. All information generated when a patient is treated by the public health service is reported here. In addition to information regarding procedures and admissions, the register contains information on residence, partner status, level of education, income, comorbidities and emigration amongst others. Operations are recorded according to the NOMESCO classification, while diagnoses are coded according to the ICD-10 classification.

Identification of primary procedures

We will determine the cohort of primary procedures from DKR (called P-DKR) by identifying all primary procedures performed from January 1st 1998 to December 31st 2021. P-DKR is then transferred to Danmarks Statistik (DS). Through DS, all primary procedures in the observation period will be identified using NOMESCO operation codes (KNGB*) and these will be collected in a cohort called P-SD. P-DKR and P-SD will be joined into a cohort called PRIM and this cohort will best describe all primary procedures performed in Denmark during the observation period.

Identification of revision procedures

The DKR cohort of revisions (R-DKR) will be identified by all registrations marked as revisions during the observation period. R-DKR is also transferred to DS. All revisions will be identified in DS as R-DS using the NOMESCO operation codes KNG* (knee procedure), KNGC* (revision of knee), KNGG* (arthrodesis) and KNFQ19 (femur amputation). The cohorts R-DKR and R-DS will be combined and called REV. This cohort will best describe revision procedures performed in Denmark during the observation period.

Insertion of cement spacers presents a special registration problem, as different registration practices exist. Some use KNGS codes (eg KNGC59A – Insertion of spacer in a knee joint in connection with revision). We intend to not consider spacer insertion as a revision. For example a two-stage revision will be considered as one revision.

Organization of data

A table (G) with PRIM and REV will be created. G will contain information on revisions, deaths, disappearances, emigration and the associated dates. For each knee joint in PRIM and for each date in the observation period, it will be possible to describe the status of the knee joint.

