#### Definition of major and minor revision

Major and minor revisions are defined as the following implant types:

- 1 = TKA
- 2 = medial UKA
- 3= lateral UKA
- 4 = patellofemoral UKA
- 5+7 = rotating hinge-prosthesis
- 6 = Resection prosthesis
- 9 = Partial resurfacing
- 10 = articulated cement spacer
- 11 = fixated cement spacer
- 100 = Rotating hinge-prosthesis with condyle resection
- 103 = Removal of patella component
- 104 = Resection or segmental prosthesis
- 105 = Hemicap
- 107 = Episealer
- 108 = Other removal
- 109 = New liner
- 110 = New patella component
- 112 = Exchange of femoral component

- 117 = Removal of tibia component
- 119 = Insertion of stemmed tibia component
- 120 = Exchange of tibia component

Laterality: Code for specifying right/left knee. 1 = right, 2 = left

Sex: Specifying the sex of the patient. M = male, F = female

Age: Number specifying the age of the patient at the time of performed procedure

Indication for primary procedure: Code specifying the indication for performing the primary procedure. The codes are:

- 1 = Idiopathic knee osteoarthritis
- 2 = Secondary arthritis
- 3 = Sequelae after tibia condyle fracture
- 4 = Sequelae after femur condyle fracture
- 5 = sequelae after patella fracture
- 6 = Rheumatoid arthritis
- 7 = Sequelae after other arthritis
- 8 = Haemophilia
- 9 = Tumour - primary
- 10 = Tumour – metastasis

Performing institution: Code specifying the performing institution. The codes are classified as SHAK-codes, developed by "Sundhedsdatastyrelsen". (<https://medinfo.dk/sks/brows.php>)

Duration of procedure: Number specifying the duration of the performed procedure. Given as minutes.

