Year	1 st revision	2 nd revision	....	n grade revision	Maximal grade of revision performed*
1998					
1999					
2000					
2001					
2002					
2003					
2004					
2005					
2006					
2007					
2008					
2009					
2010					
2011					
2012					
2013					
2014					
2015					
2016					
2017					
2018					
2019					
2020					
2021					

Only grades of revisions with occurrences >10 for all years are shown

\*The maximal grade of revision performed is defined as the single greatest grade of revision performed that year

[figure not shown]
**Figure 2.** The standardized prevalence and incidence rates of n-grade revisions from 1998 to 2021.

*Anticipated plot design, illustrating with imaginary data, A-D*

Panel A and B illustrates standardized prevalence and incidence of major n-grade revisions. Panel C and D illustrate standardized prevalence and incidence of all n-grade revisions (including both major and minor revisions). Only grades of revisions with occurrences >10 are shown; for prevalence, >n-grade revisions are reported as well.

**Figure 3.** The standardized prevalence of patients with their total sum of revisions.

Panel A illustrates standardized prevalence of patients with major n-grade revisions. Panel B illustrates standardized prevalence rates of patients with all n-grade revisions (including major and minor revisions). The total sum of revisions is the summation of all revision procedures performed on a patient. E.g., a patient with 3 revisions performed on one knee and 4 revisions performed on the other knee, is categorized as a 7-grade revision patient. Only grades of revisions with occurrences >10 are shown as well as >n-grade grade revisions.

[figure not shown]

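### The SAP's all-revision grades count a spacer stage as a revision of its own, while the protocol counts a two-stage revision once, and no deviation is declared

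*SAP*

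**What the plan says.** **Protocol, Identification of revision procedures.** After noting that hospitals register cement spacers in different ways, the protocol states its rule: "We intend to not consider spacer insertion as a revision. For example a two-stage revision will be considered as one revision". It gives KNGC59A as an example of a spacer code.

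**SAP section 3, Data management, for both registers.** The general definition is broad: "A revision is defined as the exchange, addition, or removal of a knee prosthesis component". The definition of minor revision covers liner and patella procedures and then adds: "Insertion/removal/exchange of spacers are also included in this category".

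**SAP code lists.** The Danish Knee Arthroplasty Register (DKR) list of major and minor revisions includes "10 = articulated cement spacer" and "11 = fixated cement spacer". It also includes removal entries, among them "108 = Other removal" and "117 = Removal of tibia component". The Landspatientregisteret (LPR) list of minor revisions includes KNGC59A, the protocol's own example of a spacer code.

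**SAP section 5, Figure 3.** The patient-level grade is a plain sum: "The total sum of revisions is the summation of all revision procedures performed on a patient".

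**SAP section 4.** The table of deviations from the protocol is empty.

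**The concern.** The primary outcome in the SAP's PICOTS is annual prevalence and incidence by grade of revision. The SAP's background defines a multiply revised knee as one with at least three revisions. The counting rule therefore determines the main result, and the two documents give different rules for the same procedure.

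The difference does not fall evenly across patients. The protocol's section on indications names two-stage revision as one of the two typical treatments of deep infection, and reports infection as the believed leading cause of multiple revisions. The two rules thus diverge most in the group the study is about. Since the protocol itself warns that spacer registration varies, an all-revision grade that counts spacer records would also partly measure local coding practice.

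With no deviation declared, a reader who has both documents could not tell which count lies behind the published figures.

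**Working it through.** The plan gives no figure to reproduce: the SAP reports no sample size calculation and plans no formal testing. The check is a count by rule.

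**Inputs**
- Protocol, Identification of revision procedures: a two-stage revision counts 1.
- SAP section 3: a spacer procedure is a minor revision, and exchange of the femoral and/or tibial component is a major revision. No supplied section merges stages.
- SAP background: the threshold is 3 or more on the same knee.

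**Formula.** For one knee, let *k* be the number of revision episodes, *t* the number of these done in two stages with a spacer, and *x* the number of additional spacer exchanges.
- Protocol grade = *k*. The protocol does not mention spacer exchange; I treat it as part of the same episode.
- SAP all-revision grade = *k* + *t* + *x*. This assumes that spacer removal and re-implantation in the same operation count once.

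**SAP major-only grade.** A one-stage exchange counts 1 and an isolated liner exchange 0. A two-stage revision counts 1 if only the re-implantation is major. It counts 2 if DKR marks the femoral or tibial component as revised at the first stage, because the DKR definition of major revision works from those two flags.

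| Episodes on one knee | Protocol | SAP all-revision | Major-only, first stage not flagged | Major-only, first stage flagged |
|---|---|---|---|---|
| Two-stage | 1 | 1 + 1 = 2 | 1 | 2 |
| One-stage exchange, then two-stage | 2 | 2 + 1 = 3 | 1 + 1 = 2 | 1 + 2 = 3 |
| Two two-stage | 2 | 2 + 2 = 4 | 1 + 1 = 2 | 2 + 2 = 4 |
| Isolated liner exchange, then two-stage | 2 | 2 + 1 = 3 | 0 + 1 = 1 | 0 + 2 = 2 |

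**Threshold.** With *k* = 2, any *t* of 1 or more gives an SAP all-revision grade of at least 3, so every two-episode knee with a two-stage revision crosses. With *k* = 1 and *x* = 0 the most is 2, so none crosses. One two-stage revision with one spacer exchange gives 1 + 1 + 1 = 3 and does cross.

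**Removal-only first stage.** A first stage recorded as a component removal (DKR codes 108 or 117) also raises the grade by 1 under the SAP's general definition.

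**Figure 3B.** A patient with one plain two-stage revision in each knee has a sum of 2 + 2 = 4 under the SAP. The protocol's two-stage rule applied to the same sum gives 1 + 1 = 2. The protocol defines no patient-level sum, so this only shows the effect of the rule. It is not a case of the same-knee threshold.

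**Scale, by assumption only.** Suppose a share *s* of episodes is two-stage, independently between episodes. The fraction of two-episode knees that move to grade 3 or more is then 1 − (1 − *s*)². For *s* = 5%, 10% and 20% this is 9.8%, 19.0% and 36.0%. The documents give no value of *s*, and independence is doubtful where infection recurs.

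**The case against.** The strongest reply is that the SAP never states that stages count separately. Because section 4 declares no deviation and the protocol is attached as a supplement, an analyst might merge stages under the protocol first and use the SAP's minor category only to label spacer records. It is true that separate counting is an inference. But nothing in the SAP tells the analyst to merge. Its general definition, its code lists and the Figure 3 sum all point to counting each procedure. At best the count is left undetermined, which also needs repair.

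Second, the major-only series (Table 2, Figure 2 A-B, Figure 3A, Supplementary Figures 1-5, Supplementary Tables 1-2) may be largely free of spacer counting. That stands, provided first stages are not flagged in DKR. It does not restore the protocol's count, though. Isolated liner and patella exchanges are revisions under the protocol and drop out of that series. Nor does PICOTS name the major-only series as primary.

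Third, the value of 2 for a plain two-stage revision rests on the same-operation assumption. This is fair. The SAP lists spacer removal as a minor revision and has no same-operation rule, so a literal count could reach 3. That would widen the gap.

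Fourth, the study is descriptive and the number of affected knees is unknown. Both are true. The conflict still changes the quantity being described.

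**Conclusion.** The concern holds. The SAP departs from the protocol's rule on spacers and two-stage revisions without declaring it. Followed as written, it adds one grade per spacer stage in all outputs that include minor revisions. Knees with two revision episodes, at least one of them two-stage, become multiply revised in those outputs and not under the protocol.

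This rests on three things: no merging rule in the SAP sections available, spacer removal and re-implantation at one operation counting once, and spacer stages being recorded with the listed codes. Whether the major-only series is also affected depends on how DKR flags first stages, which the documents do not show. No percentage of knees can be claimed. The point should be settled before the analysis is run.

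**What to change.** Reconcile the protocol's rule with the SAP's definition of minor revision and both code lists, in one of two ways.

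1. **Link stages before grading.** Join the first stage (a spacer record, or a removal record such as DKR 108 or 117 when followed by re-implantation) and the re-implantation in the same knee into one revision. Pre-specify the linkage window, the event date, and the handling of spacer exchanges and of knees never re-implanted. Report stage counts separately.
2. **Keep the SAP count.** Enter the change and its reason in section 4, state whether spacer removal and re-implantation at one operation count once, and show the all-revision results under both counts.

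In either case, tabulate how often the DKR femoral or tibial flag is positive on first-stage records, and apply the same linkage to the major-only series if needed.

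Smaller repairs:
- The protocol speaks of KNGS codes for spacers but gives a KNGC code as its example.
- Its search for revisions uses the KNG* wildcard, which would cover KNGS, while the LPR request list names no KNGS codes. State whether such records are held.
- The SAP's LPR minor list is described as KNGC codes but contains KNGS49, whose description is not plainly a component or spacer procedure. Justify it as a stand-alone revision or remove it.

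**Cost.** Option 1 needs SAP text, a linkage step with its rules, and the flag check. A window must be chosen, and some links will be uncertain: code 108 names no component, and the SAP's LPR lists contain no removal code. Option 2 needs a section 4 entry and a second set of all-revision outputs, and the protocol count in that set needs the same linkage. The SAP places the final analysis after its own acceptance, so either change can be made first.
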